4.2. Assumption

Data for all endpoints will be evaluated using an intention-to-treat analysis. All data will be expressed as mean \pm standard deviation. The unpaired Student's t-test and Mann-Whitney U test will be used to compare continuous variables. Categorical variables will be compared using the chi-square and Fisher's exact tests. All time-to-event outcomes of MACEs will be summarized using Kaplan-Meier survival estimates and compared between the two groups using log-rank tests. $p < 0.05$ is considered statistically significant. All statistical analyses will be performed using SPSS software (version 20.0, SPSS Inc., Chicago, IL, USA).

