5.1. Primary endpoint: the efficacy of cutting balloon

- ① Minimal stent CSA (cross-section area) with IVUS at calcium site

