Coronary angiography will be digitally recorded at baseline and immediately after the procedure (post-balloon and post-stenting) and assessed offline in the angiographic core laboratory. The quantitative coronary angiographic analysis will be performed using an automated edge-detection algorithm (CAAS-5; Pie-Medical, Best, Netherlands) with conventional methods by independent interventional cardiologists who are blinded to the type of balloon used, treatment outcomes, and IVUS analysis. All measurements will be performed using cineangiograms recorded after the intracoronary injection of nitroglycerin. The interpolated reference diameter will be considered as the reference segment diameter. The lesion length is defined as the distance from the proximal shoulder to the distal shoulder at the lesion site. Standard qualitative and quantitative analyses and definitions will be used for quantitative coronary angiography (QCA) (qca 1, 2 references).

5.3. IVUS procedure and analysis:

After regular coronary angiography, IVUS will be performed at baseline (before pre-dilatation) and repeated immediately after stent implantation in all cases. IVUS will be performed using an OptiCross 60 MHz (Scientific Corporation, Maple Grove, MN, USA). After intracoronary injection of nitroglycerin, the IVUS catheter will be carefully advanced distal to the culprit lesion under fluoroscopic guidance and then withdrawn automatically at 0.5 mm/s to perform the imaging sequence, which begins 20 mm distal to the culprit lesion and ends at the aorto-

ostial junction. IVUS imaging will be recorded on the compact disc for offline analysis by a single experienced observer who is unaware of the clinical and angiographic information. IVUS measurements will be performed in accordance with the American College of Cardiology Clinical Expert Consensus Document on the Standards for Acquisition, Measurement, and Reporting of Intravascular Ultrasound Studies. The ischemia-related vessel is identified as narrow ($\geq 70\%$) using angiography. The culprit lesion site selected for analysis is the image slice with the lowest luminal cross-sectional area (CSA). The proximal and the distal reference segments are defined as the most normal-looking cross-sections within the same arterial segment, typically ≤ 10 mm from the lesion, but before any large side branch.

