7.1. Inclusion criteria

- 1) coronary artery disease including in-stent restenosis (ISR) or de novo lesion with stenosis of $\geq 70\%$,
- 2) target lesion calcification confirmed by an imaging study: various degrees of calcium deposition along the coronary artery wall (an arch of calcium at least 100 degrees) confirmed at baseline coronary angiography, computed tomography, and IVUS),
- 3) reference vessel diameter between 2.0 and 4.0 mm, deemed suitable for percutaneous coronary intervention (PCI).

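### The primary endpoint, an absolute stent area, is compared without adjustment for baseline vessel size, forgoing precision that could be had at almost no cost

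*Combined protocol and SAP*

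**What the plan says.** Section 5.1 (Primary endpoint) defines the primary endpoint as "Minimal stent CSA (cross-section area) with IVUS at calcium site". It is an absolute area, not indexed to the size of the vessel.

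Section 4.2 (Assumption) gives the whole analysis of continuous variables: the unpaired "t-test and Mann-Whitney U test will be used to compare continuous variables", with p < 0.05 as the criterion. No regression model, covariate or stratification factor is named anywhere, and neither a confidence interval nor a noninferiority margin is stated.

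Section 7.1 (Inclusion criteria) admits a "reference vessel diameter between 2.0 and 4.0 mm, deemed suitable for percutaneous coronary intervention (PCI").

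Baseline vessel size can be obtained from imaging already planned:
- Section 5.3 (IVUS procedure and analysis): "IVUS will be performed at baseline (before pre-dilatation) and repeated immediately after stent implantation in all cases". Also: "IVUS imaging will be recorded on the compact disc for offline analysis by a single experienced observer". Reference segments are defined there too: "The proximal and the distal reference segments are defined as the most normal-looking cross-sections within the same arterial segment".
- Section 5.2 (Quantitative coronary angiography): "Coronary angiography will be digitally recorded at baseline and immediately after the procedure". Also: "The interpolated reference diameter will be considered as the reference segment diameter".

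Section 5.3 also defines stent expansion (minimum stent CSA over reference lumen CSA) and acute CSA gain. Neither is a listed endpoint, and acute gain subtracts the baseline minimum CSA, which is not a measure of vessel size.

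**The concern.** A larger vessel would be expected to take a larger stent, so part of the between-patient spread in minimal stent CSA may reflect vessel size and have nothing to do with the balloon used. By defining stent expansion, the plan itself treats reference lumen area as relevant to stent area. The unadjusted comparison nevertheless leaves all of that spread in the error term.

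The hypothesis in section 4.1 is noninferiority, and such a conclusion is drawn from a confidence limit. Width that could have been removed by a baseline measurement works directly against that conclusion. The loss is one of efficiency: under random allocation the unadjusted test remains valid.

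**Working it through.** **Inputs from the documents.** Reference diameter 2.0 to 4.0 mm (section 7.1). Means 6.26 and 5.03, difference 1.23 (section 4.1; printed in mm, though an area is in mm²). Two-sided α = 0.05, β = 0.2, 20% loss (section 4.1). 125 per arm (section 4.3), against 250 per arm proposed in section 4.1.

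**Not in the documents, so assumed.** SD of stent CSA (1.5 to 3.1 mm²), noninferiority margin (0.25 to 1.0 mm²), and R², the share of within-arm variance in stent CSA explained by baseline vessel size (0 to 0.50).

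**1. The plan's sample size.** The total of 250 cannot be reproduced, because no SD is given. Treated as a superiority comparison of 1.23, it follows only from a back-solved SD of about 3.10: n per arm = 2 × [(1.96 + 0.842) × 3.10 / 1.23]² = 99.7, so 100; 200 / 0.8 = 250. That value serves here only as the upper end of the SD range.

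**2. Spread of vessel size.** Area = π/4 × D²: 3.14 mm² at 2.0 mm and 12.57 mm² at 4.0 mm, a fourfold range.

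**3. Width of the interval.** Half-width in SD units = 1.96 × √(2/n) × √(1 − R²).

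| R² | √(1 − R²) | Narrower by | 100/arm | 125/arm | 250/arm |
|---|---|---|---|---|---|
| 0 | 1.000 | – | 0.277 | 0.248 | 0.175 |
| 0.10 | 0.949 | 5% | 0.263 | 0.235 | 0.166 |
| 0.20 | 0.894 | 11% | 0.248 | 0.222 | 0.157 |
| 0.30 | 0.837 | 16% | 0.232 | 0.207 | 0.147 |
| 0.50 | 0.707 | 29% | 0.196 | 0.175 | 0.124 |

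The percentages need no SD. The equivalent sample-size multiplier is 1/(1 − R²): 1.11, 1.25, 1.43 and 2.00. At R² = 0.50, 125 per arm gives the precision of 250 per arm unadjusted.

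**4. Cost if the covariate is useless.** With R² = 0, the expected inflation from chance imbalance is √(1 + 1/(2n − 4)). At n = 125 this is √(1 + 1/246) = 1.002, or 0.2% wider. Simulation with a normal outcome and covariate and 1:1 random allocation (4,000 runs per setting, 125 per arm) gave adjusted-to-unadjusted half-width ratios of 1.002, 0.951, 0.896, 0.838 and 0.709 for the five R² values, with adjusted coverage about 95% throughout.

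**5. Effect on noninferiority power at 125 per arm.** Power = Φ[(d + margin) / (SD × √(2/n) × √(1 − R²)) − 1.96], where d is the true difference in favour of the cutting balloon.

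| d | SD | Margin | R² = 0 | R² = 0.30 |
|---|---|---|---|---|
| 1.23 | 3.1 | 0.25 | 96.5% | 99.5% |
| 0 | 2.0 | 0.25 | 16.6% | 21.8% |
| 0 | 2.0 | 0.5 | 50.7% | 65.6% |
| 0 | 2.0 | 1.0 | 97.7% | 99.7% |
| 0 | 3.1 | 0.25 | 9.3% | 11.5% |
| 0 | 3.1 | 0.5 | 24.7% | 33.1% |
| 0 | 3.1 | 1.0 | 72.2% | 86.2% |

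The first row is the lowest-power case at d = 1.23. Over the whole assumed range, R² = 0.30 adds at most 3 points at d = 1.23 and 0 to 15 points at d = 0. At d = 0 and R² = 0.10, the largest gain is 4.6 points.

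**The case against.** The strongest reply is that this is a preference and not an error. A two-sample comparison is an acceptable primary analysis of a continuous endpoint and is valid under randomisation. That stands, and it limits the weight of the point.

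Second, at the only effect the plan cites the adjustment is nearly irrelevant. With a difference of 1.23 and 125 per arm, unadjusted power is already at least 96.5%; with 250 per arm it is above 99.9%, and R² = 0.30 adds less than 0.04 points. This also stands. But the stated hypothesis is noninferiority, and section 4.1 itself notes that similar trials have disagreed, so it is unsafe to plan only for the favourable case.

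Third, R², SD and margin are all assumed, and an eligibility range is not a distribution. Suppose, for illustration, that stent area is 0.8 of reference area on average and the total SD is 3.10. A uniform 2 to 4 mm diameter (SD of area 2.73 mm²) then gives a correlation of 0.8 × 2.73 / 3.10 = 0.70. A normal diameter with mean 3.0 and SD 0.35 mm (SD of area 1.66 mm²) gives 0.8 × 1.66 / 3.10 = 0.43. The gain could therefore be modest, and no R² shown above is put forward as the likely one. What remains is the asymmetry: about 0.2% to lose against 5% to 29% to gain.

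Fourth, the plan states no confidence interval or margin to sharpen. That is a larger, separate gap. It does not undo this point, because any noninferiority conclusion will need a confidence limit.

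Fifth, the documents describe the study as randomised and observational (section 1) and as a matched cohort (section 4.1). If it is matched or not random, a simple unpaired model is not sufficient. That stands and is carried into the fix.

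**Conclusion.** The point holds as an inexpensive improvement that should be made. It is not a flaw that invalidates the plan. The endpoint is an absolute area, the planned comparison is unadjusted, and a suitable baseline covariate can be read from imaging already scheduled in every patient.

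The interval narrows by the factor √(1 − R²), and the documents do not allow R² to be estimated. The practical effect on the conclusion ranges from almost none, if the true difference is near 1.23, to as much as 15 points of power at zero true difference with R² = 0.30 and an unfavourable combination of assumed SD and margin.

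Describing this as lost precision and not bias assumes random allocation. If allocation is not random, lack of adjustment is also a bias concern, and adjusting for this one covariate would not remove that bias.

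**What to change.** Prespecify in section 4.2, before any outcome data are seen:

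> The primary analysis is a linear model of minimal stent CSA on treatment group and reference lumen CSA read on the pre-dilatation IVUS pullback (mean of the proximal and distal references, or the single measurable value). The adjusted mean difference with two-sided 95% CI is the primary result. The unadjusted t-test and Mann-Whitney test are sensitivity analyses.

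- The baseline QCA reference diameter is an alternative covariate. Name one in advance and use it for all patients.
- The value must be taken before pre-dilatation, because a post-stent reference could be affected by treatment.
- State a rule for missing baseline values, for example a value predicted from baseline QCA reference area, or the pooled mean, assigned blind to arm.
- Once a margin is stated, compare it with the confidence limit from this model.
- Settle the allocation method first. If patients are matched, the model must reflect the pairing, and the extra gain is smaller if pairs are matched on vessel size.

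The cost is a few SAP sentences and one degree of freedom, with no extra patients or imaging. The plan does not say which pullback supplies the reference lumen CSA, so the single IVUS observer may have some additional baseline reading to do.

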5.2. Secondary endpoint: comparing the clinical outcomes

- ① MACE (major adverse cardiac events): composite of death, MI, TVR at 1yr follow-up
- ② TLR (target lesion revascularization) at 1yr follow-up
- ③ Procedure time, the total amount of contrast, and the number of balloons

3. Analysis plan

- 6.1. Study period: 24 months
- 6.2. Enrollment: 12 months
- 6.3. Follow-up: 12 months
- 6.4. Analysis and result report: 2 months

4. Sample size calculation for the primary analysis

4.1. Hypothesis:

This trial is a 1:1 matched comparative cohort clinical trial, with patients being assigned to either the cutting balloon or the NC balloon group (1: 1 ratio) during the study period. It will test the noninferiority of a strategy of cutting balloon pre-dilatation compared with NC balloon pre-dilatation in the treatment of calcified coronary lesion. minimal CSA at the calcium site assessed by IVUS is the primary endpoint. Limited similar clinical trials on cutting balloon for the treatment of de novo various degree calcified coronary lesions have achieved differing results. The result of a previous study that investigates the efficacy of cutting balloon indicates that the mean CSA after cutting balloon treatment for native coronary artery disease are 6.26mm and 5.03 mm in the NC balloon group (18). We hypothesize that stent implantation after the cutting balloon pre-dilatation will not be inferior to pre-dilatation with NC balloon for the treatment of de novo calcified coronary lesions. Using double-sided inspection, $\alpha = 0.05$ and $\beta = 0.2$, and considering the expected loss to follow-up of 20%, the number of cases to be included should be at least 250. Therefore, we aim for 125 cases for each group. Nevertheless, the sample size proposed was 250 patients in each group to further increase the power and account for possible protocol deviation.

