4.3. Final sample size

Total number = 250 (Wolverine cutting balloon = 125, Non-compliant balloon = 125)

5. Methods

5.1. PCI procedure and medication:

PCI and stent implantation will be performed according to the current guidelines using standard interventional techniques (reference). Before PCI, all patients will be administered loading doses of aspirin (200–300 mg), clopidogrel (300–600 mg), ticagrelor (180 mg), or prasugrel (60 mg). After sheath insertion at the arterial access site, weight-adjusted unfractionated heparin will be administered at a bolus dose of 100 U/kg, with an additional bolus to maintain an activated clotting time of 250–300 s. Additional intravenous and intracoronary injections of platelet glycoprotein IIb/IIIa receptor blockers will be administered at the discretion of the operator. The interventional strategy, balloon size, and stent selection will be based on the discretion of the same operator for all patients. However, modification of the calcific atheroma using rotational atherectomy can be performed at the operator's discretion in cases of balloon-uncrossable lesions, and these cases will be excluded from enrollment. All patients who undergo PCI will receive aspirin (100 mg daily) with clopidogrel (75 mg daily), ticagrelor (180 mg), or prasugrel (60 mg) because a dual antiplatelet

maintenance regimen for at least 12 months is recommended. Cilostazol (100–200 mg daily) will be administered as an adjunct to the dual antiplatelet regimen at the treating physician's discretion. In-hospital stay and after-discharge medications include aspirin, clopidogrel, ticagrelor, prasugrel, beta-blockers, calcium channel blockers, angiotensin-converting enzyme inhibitors, angiotensin receptor blockers, and lipid-lowering agents such as statins, which will be recorded and entered into a dedicated computerized database with clinical information.

5.2. Quantitative coronary angiography:

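### One-year MACE is compared between arms by a log-rank p-value alone; without a between-arm estimate and confidence interval, a non-significant result would not show which differences the data rule out

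*Combined protocol and SAP*

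**What the plan says.** The secondary objective in the Study Outcomes section is headed "Secondary endpoint: comparing the clinical outcomes". Its first item is "MACE (major adverse cardiac events): composite of death, MI, TVR at 1yr follow-up", followed by TLR at one year.

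Section 4.2 gives the whole method for MACE: its time-to-event outcomes will be "summarized using Kaplan-Meier survival estimates and compared between the two groups using log-rank tests". A p-value below 0.05 "is considered statistically significant". The other tests named there are the t-test, Mann-Whitney, chi-square and Fisher's exact. No between-arm effect measure or confidence interval is planned for any endpoint. TLR is not named, so it is unclear whether it falls under the log-rank sentence or the one on categorical variables.

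The sample size is derived in section 4.1 for the IVUS cross-sectional area, with 20% expected loss. No MACE rate, event target, power or margin is stated. Section 4.3 gives "Total number = 250 (Wolverine cutting balloon = 125, Non-compliant balloon = 125". Section 4.1 reaches the same 125 per group, but then proposes 250 in each group.

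**The concern.** A log-rank test says whether the curves differ by more than chance would explain. It gives neither the size of the difference nor the range of differences the data allow. The trial is sized on an imaging measure, so the number of clinical events will be whatever that size yields, and a non-significant MACE result could come from arms that are truly alike or from too few events.

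The stake is interpretation. The trial's hypothesis is noninferiority on stent area. If that is met and MACE is reported beside it with p > 0.05, a reader may conclude that the cutting balloon is clinically no worse. The same data could be compatible with a doubled hazard, and the analysis as written would not report that. Nothing in the plan guards against the misreading.

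**Working it through.** **The plan's own figure.** There is none for MACE. The total of 250 belongs to the area endpoint and cannot be reproduced, because no SD or margin is given. A two-sided comparison of 6.26 with 5.03 at 80% power would need an SD of about 3.1 to give 100 per group, and 100/0.8 = 125. This has no bearing on MACE beyond fixing the number of patients.

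**Inputs from the documents.**
- 125 per group (section 4.3), or 250 per group (last sentence of section 4.1).
- 20% loss (section 4.1).
- 12 months of follow-up.
- Significance at 0.05, taken as two-sided.

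**Assumptions.**
- One-year MACE of 5, 8, 10 or 15%.
- Loss spread evenly over the year, so about 10% of information is lost. Effective n per group is 125 × 0.9 = 112.5, or 250 × 0.9 = 225.
- Proportional hazards.

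**Step 1: power if one arm has twice the hazard.** Let p be the risk in the lower-risk arm. The other arm's risk is p1 = 1 − (1 − p)², which is 9.75, 15.36, 19.0 or 27.75%. Expected events are d = n × (p + p1). Power (Schoenfeld, 1:1) is Φ(½ × √d × ln 2 − 1.96). For example, at p = 5% and 125 per group, d = 112.5 × 0.1475 = 16.6 and power = Φ(−0.55) = 29%.

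| MACE, lower-risk arm | Events, 125/group | Power | Events, 250/group | Power |
|---|---|---|---|---|
| 5% | 17 | 29% | 33 | 51% |
| 8% | 26 | 43% | 53 | 71% |
| 10% | 33 | 51% | 65 | 80% |
| 15% | 48 | 67% | 96 | 92% |

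A simulated log-rank test (exponential times, 20% loss, 4,000 runs) agrees. At 5, 10 and 15% it gives 27, 50 and 66% with 125 per group, and 48, 78 and 91% with 250. Under Schoenfeld, 50% power needs about 32 events and 80% needs 66.

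**Step 2: precision if the arms are truly equal.** Expected events are d = 2 × n × p. The 95% interval for the hazard ratio is the estimate divided and multiplied by exp(1.96 × 2/√d). The half-width for the 1-year risk difference is 1.96 × √(2p(1 − p)/n). With 125 per group:

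| MACE, both arms | Events | HR factor | Half-width of risk difference |
|---|---|---|---|
| 5% | 11 | 3.2 | 5.7 points |
| 8% | 18 | 2.5 | 7.1 points |
| 10% | 23 | 2.3 | 7.8 points |
| 15% | 34 | 2.0 | 9.3 points |

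So an observed hazard ratio of exactly 1.0 would still allow a doubling at 5, 8 and 10%. At 15% the upper limit is 1.96, which just excludes it. With 250 per group the factors are 2.3, 1.9, 1.8 and 1.6, so only the 5% case still allows a doubling. These are normal approximations and are rough at 11 events.

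The event counts in the two steps differ because the scenarios differ. The 11 to 34 events assume equal arms and must not be paired with the power figures, which belong to 17 to 48 events.

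**The case against.** MACE is a secondary endpoint and is not powered. The noninferiority hypothesis is tied to stent area, and the documents nowhere say that a non-significant MACE result will be read as comparability. The effect estimate needs no new data and could be added at analysis. All of this stands, and it keeps the point to one of reporting. It does not remove it: an unpowered comparison is where a p-value alone says least, and naming the effect measure now fixes the choice before results are seen.

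A reader might infer more than the documents support, in three ways.

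- *That a non-significant result is likely even if the hazard is doubled.* With 125 per group this holds at 5 to 8% MACE. At 10% it is about even, and at 15% a significant result is more likely. With 250 per group it does not hold at any of the four rates: power is about even at 5% and 71% or more above that. No rate is given, so no single statement is safe.
- *That the planned analysis tells readers nothing about the clinical comparison.* Kaplan-Meier estimates are planned for each arm, so both 1-year rates and their crude difference can be read off. What is missing is a formal contrast with its uncertainty.
- *That the plan claims clinical equivalence.* It does not. The risk lies in how a null result may be read.

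**Conclusion.** The gap holds at any sample size and any event rate: section 4.2 plans a test of MACE but no between-arm estimate or interval, so a non-significant result would not show what difference the data exclude. How much this matters depends on two things the documents leave open. One is the MACE rate, assumed here at 5 to 15%. The other is the number of patients, on which sections 4.1 and 4.3 disagree. Across those ranges, power against a doubled hazard runs from 29% to 92%. At the 125 per group given as the final size, it is about even or worse at MACE rates up to 10%. This is a cheap improvement to the analysis section and not a flaw in the design. It gives no reason to enrol more patients for MACE.

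**What to change.** In section 4.2:

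- **MACE.** Make the between-arm difference in 1-year Kaplan-Meier cumulative incidence, with 95% CI, the main result. Add a Cox hazard ratio with 95% CI. Keep the log-rank p-value as supportive.
- **TLR.** Name the method. Death is part of MACE but competes with TLR, and one minus Kaplan-Meier with deaths censored overstates TLR incidence. Report the difference in 1-year cumulative incidence with death as a competing event (Aalen-Johansen) and a cause-specific hazard ratio, each with 95% CI.
- **Interpretation.** State that p > 0.05 for a clinical outcome will not be reported as similar or comparable outcomes, and that interpretation rests on the confidence limits.
- **Context.** State the MACE rate assumed, and reconcile the sample sizes in sections 4.1 and 4.3 so that the expected precision can be given.

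The cost is a few sentences and a few lines of analysis code, with no new data or visits. The downside is that wide intervals will be shown, and the clinical result will look less reassuring than a bare p-value.
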